8.3.8 EVENTS OF SPECIAL INTEREST

Not Applicable

8.3.9 REPORTING OF PREGNANCY

Not Applicable

8.4 UNANTICIPATED PROBLEMS

8.4.1 DEFINITION OF UNANTICIPATED PROBLEMS (UP)

Not Applicable

8.4.2 UNANTICIPATED PROBLEM REPORTING

Not Applicable

8.4.3 REPORTING UNANTICIPATED PROBLEMS TO PARTICIPANTS

Not Applicable

9 STATISTICAL CONSIDERATIONS

9.1 STATISTICAL HYPOTHESES

• Primary Efficacy Endpoint(s):

Knee Society Scores will be obtained prior to surgery, and at 8 weeks postoperatively

- Objective knee score (completed by the surgeon)
- Subjective knee score (completed by patient)
- Secondary Efficacy Endpoint(s):

All outcomes will be measured at 8 week postoperative visit or the visit closest to this time point

Outcomes for all patients regardless of discharge location

• Number of outpatient visits to a physical therapy center

Outcomes for patients discharged to inpatient rehabilitation

o Number of inpatient days in a rehabilitation center

Outcomes for patients randomized to the X4 brace with the Motion Intelligence platform

- Patient satisfaction with the X4 brace with the Motion Intelligence platform: Patients will complete the System Usability Scale (SUS)
- Compliance in using the X4 brace with the Motion Intelligence platform: Patients will be instructed to use the X4 brace twice a day. For each day, a subject will be considered compliant if they access the platform at least once a day, and non-compliant if they do not access at all the platform that day.
- Adherence using the X4 brace with the Motion Intelligence platform: For each day, a subject will be considered adherent if they perform the entire exercise routine as prescribed at least once a day, and non-adherent if they do not perform the entire exercise routine that day.
- Primary Safety Endpoint(s)
- Adverse Events related to the X4 brace will be collected in patients regardless of discharge location.

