1 PROTOCOL SUMMARY

1.1 SYNOPSIS	
Title:	A phase 4, prospective, randomized trial to evaluate postoperative outcomes in total knee arthroplasty (TKA) patients using the DJO X4 brace with the Motion Intelligence Platform
Study Description:	This is a single center, investigator initiated clinical trial using a FDA approved, marketed brace called DJO X4. This phase 4, prospective, randomized clinical trial is being conducted to evaluate the use of the X4 knee brace with the Motion Intelligence platform in patients having unilateral TKA. The study is designed to determine if using a "virtual rehabilitation" device leads to enhanced recovery following TKA by improving patient objective and subjective outcome measures. These primary outcomes will be collected using a validated tool called the Knee Society Score (KSS) (Appendix A).
	 Cohort 1- Study group-Home discharge. Patients randomized to this group will be provided with the X4 brace and trained on the use of Motion Intelligence platform. Cohort 2- Control group-Home discharge. Patients randomized to this group will serve as the control group. There will be no changes to the standard of care recovery for a TKA patient. Cohort 3- Study group-Inpatient rehabilitation. Patients randomized to this group will be provided with the X4 brace and trained on the use of Motion Intelligence platform.

	 Cohort 4- Control group-Inpatient rehabilitation. Patients randomized to this group will serve as the control group. There will be no changes to the standard of care recovery for a TKA patient.
Objectives:	The aim of this study is to determine if using the X4 brace with the Motion Intelligence platform will provide enhanced, cost-effective postoperative recovery following total knee arthroplasty
	Objectives-Primary: Efficacy
	 To determine if patient postoperative outcomes, measured by the Knee Society Score, are improved by using the X4 brace with the Motion Intelligence platform
	Objectives-Primary: Safety
	To monitor the patient for any device related adverse events
	Objectives-Secondary: Efficacy
	 To determine if there is a reduction in the rehabilitation costs (inpatient or outpatient) by using the X4 brace with the Motion Intelligence platform
	 To evaluate patients satisfaction with the X4 brace with the Motion Intelligence platform
	• To evaluate patients compliance and adherence using the X4 brace with the Motion Intelligence platform

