3 OBJECTIVES AND ENDPOINTS

OBJECTIVES	ENDPOINTS	JUSTIFICATION FOR ENDPOINTS
Primary		
 To determine if patient postoperative outcomes, measured by the Knee Society Score, are improved by using the X4 brace with the Motion Intelligence platform To monitor the study group for any device related adverse events 	 To compare the Knee Society Scores, both objective and subjective scores, done preoperatively and at 8 weeks postoperatively between the control and study groups To monitor the study group for any device related adverse events 	The Knee Society Score is a validated tool used for assessing outcome in total arthroplasty patients Patients will be followed to ensure there are no issues with the utilization of the X4 brace
Secondary		
 To determine if there is a reduction in the rehabilitation costs (inpatient or outpatient) by using the X4 brace with the Motion Intelligence platform 	 To compare the number of inpatient days in a rehabilitation center between the control and study groups To compare the number of outpatient visits to a physical therapy center between the control and study groups 	To evaluate if the X4 brace provides user- friendly, cost-effective, enhanced patient recovery following total knee arthroplasty
 To evaluate patients satisfaction with the X4 brace with the Motion Intelligence platform 	 To evaluate patient's satisfaction with the X4 brace with the Motion Intelligence platform via the "System Usability Scale" (SUS) questionnaire (study group only) 	
 To evaluate patients compliance and adherence using the X4 brace with the Motion Intelligence platform 	• To measure patient's compliance using the X4 brace with the Motion Intelligence platform by counting how many days they used the platform as prescribed within an 8 week period. A patient will be	

OBJECTIVES	ENDPOINTS	JUSTIFICATION FOR
		ENDPOINTS
	considered compliant if they use the platform once a day.	
	 To measure patient's adherence using the X4 brace with the Motion Intelligence platform. Adherence is defined as performing the entire exercise routine as prescribed once a day. 	
 To evaluate provider satisfaction using the X4 brace with the Motion Intelligence platform 	 To evaluate provider satisfaction with the X4 brace with the Motion Intelligence platform via the "System Usability Scale" (SUS) questionnaire (study group only) 	In order for this technology to become part a postoperative regime the platform should be both effective and user friendly for the provider

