4 STUDY DESIGN

4.1 OVERALL DESIGN

Hypotheses: The X4 brace with the Motion Intelligence platform will provide an enhanced, cost-effective postoperative recovery following total knee arthroplasty (TKA).

This is a prospective, randomized clinical trial to evaluate the use of the X4 knee brace with the Motion Intelligence platform in patients having unilateral TKA. This brace is a FDA approved, marketed product being used as per the manufacturer's (DJO) marketed indications. Patients will be randomized to one to 4 cohorts:

This study is designed to determine if using a "virtual rehabilitation" device leads to enhanced recovery following total knee arthroplasty by improving patient objective and subjective outcome measures. These outcomes will be collected using a validated tool called the Knee Society Score (KSS)

(Appendix A). The KSS is a standard of care tool collected for all TKA patients pre-operatively and postoperatively at the 8 week visit.

- Cohort 1- Study group-Home discharge. Patients randomized to this group will be provided with the X4 brace and trained on the use of Motion Intelligence platform.
- Cohort 2- Control group-Home discharge. Patients randomized to this group will serve as the control group. There will be no changes to the standard of care recovery for a TKA patient.
- Cohort 3- Study group-Inpatient rehabilitation. Patients randomized to this group will be provided with the X4 brace and trained on the use of Motion Intelligence platform.
- Cohort 4- Control group-Inpatient rehabilitation. Patients randomized to this group will serve as the control group. There will be no changes to the standard of care recovery for a TKA patient.

No interim analysis is planned for this study. Randomization schedule will be done by the statistician via RedCap.

The DJO X4 brace will be provided to the patient at no cost. Study visits, hospitalization, inpatient and outpatient rehabilitation costs are standard of care and will be the responsibility of the patient. There will be no payment for participation in this study.

All study patients will complete a daily "Daily Patient Log" (Appendix B) starting the day after discharge from the hospital until postoperative day (POD) 56. This log will document the patient's location:

- o Rehabilitation center or
- Home physical therapy or
- Physical therapy center
- Hospital (re-admission)
- Return to work (if applicable)

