8 STUDY ASSESSMENTS AND PROCEDURES

8.1 EFFICACY ASSESSMENTS

Study Cohort Patients Only (Patients randomized to the X4 brace with the Motion Intelligence platform):

Patients will follow the prescribed exercises available on the patient application, with a number of the exercises actively tracked by the Mi360 sensor housed in the X4 brace. Compliance will be monitored by the physician and/or a delegated medical professional between postoperative visits on the Motion Intelligence dashboard.

Range of motion in flexion and extension will be measured twice daily within the patient application using the Mi360 sensor housed in the X4 brace. This information is then graphically presented on the home screen in the patient application over time. Range of motion can be tracked in real-time between postoperative visits by the physician and/or a delegated medical professional between postoperative visits on the Motion Intelligence dashboard.

Patient's will be required to access the application twice daily to enter their pain scores using the visual analog scale (0-10). Patient pain can be tracked in real-time by the physician and/or a delegated medical professional between postoperative visits on the Motion Intelligence dashboard.

All study patients:

All study patients will complete a daily "Daily Patient Log" starting the day after discharge from the hospital until postoperative day (POD) 56. This log will document the patient's location:

- Rehabilitation center or
- Home physical therapy or
- Physical therapy center
- Hospital (readmission)
- o Return to work (if applicable)

All study patients will be required to complete a preoperative and 8 week postoperative Knee Society Score questionnaire. This questionnaire is a standard of care for all total knee arthroplasty patients having surgery by Drs. [name] and [name].

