9.4.3 ANALYSIS OF THE SECONDARY ENDPOINT(S)

Secondary Outcomes: Efficacy

Outcomes for all patients regardless of discharge location:

The association between number of outpatient visits to a physical therapy center and intervention group will be examined using Poisson regression. Discharge location (home, inpatient rehabilitation) will also

be included in the model. If the interaction between intervention group and discharge location is significant, then pairwise comparisons of intervention group within each discharge location will be examined within the Poisson regression model. If the Poisson model does not fit the data well, alternative methods for count data will be considered.

Outcomes for patients discharged to inpatient rehabilitation:

Number of inpatient days in a rehabilitation center

The association between number of inpatient days in a rehabilitation center and intervention group will be examined using Poisson regression. If the Poisson model does not fit the data well, alternative methods for count data will be considered.

Outcomes for patients randomized to the X4 brace with the Motion Intelligence platform:

The association between patient satisfaction with the X4 brace, as measured by the SUS scale, and discharge location (home, inpatient rehabilitation) will be examined using the two sided, two sample t-test. If the usual assumptions required for the t-test are not met, either a suitable transformation, or an appropriate nonparametric method will be used.

The association between number of days of compliance and discharge location will be examined using Poisson regression. If the Poisson model does not fit the data well, alternative methods for count data will be considered.

The association between number of days of adherence and discharge location will be examined using Poisson regression. If the Poisson model does not fit the data well, alternative methods for count data will be considered.

Other outcomes:

Provider satisfaction with the X4 brace, as measured by the SUS scale will be described by calculating summary statistics (median, 25th percentile, 75th percentile, minimum and maximum).

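### Rehabilitation-center days are analyzed only in patients first discharged to inpatient rehabilitation, and no planned between-arm analysis shows later admissions from home or stays cut short by readmission

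*Combined protocol and SAP*

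**What the plan says.** The objective is stated in section 1.1: "To determine if there is a reduction in the rehabilitation costs (inpatient or outpatient) by using the X4 brace". The matching endpoint in section 3 is "To compare the number of inpatient days in a rehabilitation center between the control and study groups". Section 1.1 words the endpoint in the same way. Neither place restricts it by discharge location.

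Section 9.1 does. It lists outpatient physical therapy visits as an outcome for everyone, but puts "Number of inpatient days in a rehabilitation center" under the heading "Outcomes for patients discharged to inpatient rehabilitation". Section 9.4.3 keeps that split: "The association between number of inpatient days in a rehabilitation center and intervention group will be examined using Poisson regression", within the inpatient-rehabilitation group only. The outpatient-visit model in the same section takes all patients and includes discharge location. For rehabilitation-center days, no rule covers a patient who is transferred back to hospital.

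On data collection, section 8.1 says: "All study patients will complete a daily 'Daily Patient Log' starting the day after discharge from the hospital until postoperative day (POD) 56". Sections 4.1 and 8.1 list hospital readmission as a log location separate from the rehabilitation center. No endpoint or analysis in section 9 uses the readmission entry.

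**The concern.** Two kinds of patient are handled in a way that a reader of section 3 would not expect.

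- **Discharged home, later admitted to a rehabilitation center.** This patient incurs inpatient rehabilitation cost, which the objective names, but is outside the analysis of it.
- **Discharged to rehabilitation, then readmitted to hospital before the stay is complete.** Only rehabilitation-center days count, so the total can fall because of a complication. It then cannot be told apart from a short, successful stay.

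Nothing else planned would bring this to light. The safety analysis in section 9.4.4 covers patients randomized to the X4 brace only. Section 8.3.5 keeps expected postoperative events out of the eCRF and foresees no study-related events in controls. There is therefore no planned comparison of readmission between arms. Section 2.1 proposes the brace as a way to monitor readiness for discharge from rehabilitation, and section 6.3 says that investigators and participants are not blinded. Shorter stays are thus an effect that the device might plausibly produce, and a reader will want to know whether fewer rehabilitation days came with more readmissions.

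**Working it through.** **The plan's own figure.** The only sample-size calculation (section 9.2) is for the KSS subjective score: difference 10, SD 27.5, two-sided 0.05, 80% power. The normal approximation gives n = 2 × (1.960 + 0.842)² × 27.5² / 10² ≈ 119 per group. The noncentral t gives 119.7, rounded up to 120, with power 0.801. The stated 120 per group is reproduced. It has no bearing on this endpoint, for which the plan gives no figure.

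**Who is analyzed.** Section 2.1 puts discharge to acute or sub-acute rehabilitation at about 41%, and section 9.2 gives 240 patients. Assuming that the 41% applies to the trial population:
- inpatient-rehabilitation stratum: 0.41 × 240 = 98.4, about 49 per arm;
- home stratum: 240 − 98.4 = 141.6, about 71 per arm (59%), not analyzed for this endpoint.

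**Days missed in the home stratum.** The documents give no rate of later admission. Assume that 2% to 10% are later admitted for 5 to 14 days each:
- low end: 141.6 × 0.02 = 2.8 patients; × 5 days = 14 days;
- high end: 141.6 × 0.10 = 14.2 patients; × 14 days = 198 days.

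These are totals over both arms. They measure what goes unrecorded in the analysis and do not estimate bias.

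**Effect of readmission on the counted days.** Let r be the share of patients transferred to hospital in an arm, and f the share of the rehabilitation stay lost per transfer. Mean counted days are then m(1 − rf), where m is the mean uninterrupted stay.
- Same r and f in both arms: ratio = (1 − rf)/(1 − rf) = 1. Nothing is distorted.
- Every transferred patient returns and completes the stay (f = 0): ratio = 1.
- One arm has excess transfers d over an arm with none, with f = 0.5 assumed: ratio = 1 − 0.5d. For d = 2%, 5% and 10% this gives 0.990, 0.975 and 0.950.

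**The same patients with readmission days added.** With h hospital days per transfer, the ratio is [m(1 − 0.5d) + dh]/m. For d = 10%:

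| m (days) | h (days) | Rehabilitation only | Rehabilitation + readmission |
|---|---|---|---|
| 14 | 3 | 0.950 | (13.3 + 0.3)/14 = 0.971 |
| 10 | 5 | 0.950 | (9.5 + 0.5)/10 = 1.000 |
| 7 | 7 | 0.950 | (6.65 + 0.7)/7 = 1.050 |

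The values of d, f, m and h are all assumptions. The table shows that the two counts can differ, and under some inputs point in opposite directions. It does not show that they will.

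**The case against.** The case for the plan is strong in several respects.

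- **The restricted comparison is sound.** Under sections 6.1.1 and 6.3, patients are randomized after discharge location is confirmed, 1:1 within each stratum. A reader might infer that analyzing only the inpatient stratum introduces selection bias. It does not, because the stratum is fixed before assignment.
- **The count matches the objective as worded.** The objective concerns rehabilitation costs, and acute hospital days are not rehabilitation days. A patient with five rehabilitation-center days is correctly scored five. A reader might infer that the endpoint is mis-scored, or that it counts hospital days as savings. The documents do not support either reading: hospital days are simply outside the endpoint, in both strata.
- **Distortion needs a difference between arms.** With similar readmission in both arms the ratio is unaffected. The 0.950 illustration needs a 10-point excess in one arm, all during the rehabilitation stay. The log runs to postoperative day 56, so some readmissions may fall after the stay has ended and cost no rehabilitation days.
- **A combined total has weaknesses of its own.** It adds hospital and rehabilitation days as if they were equal units, and the home stratum will contribute mostly zeros. The log is completed by patients and may be incomplete during a readmission.

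All of this stands, and it limits the point to a secondary endpoint. It does not settle the mismatch between sections 1.1 and 3 and sections 9.1 and 9.4.3. Nor does it answer the home patient later admitted to a rehabilitation center, whose days are rehabilitation days on any reading. It also leaves readmission without a comparison between arms.

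**Conclusion.** The point holds as a modest, inexpensive improvement to a secondary endpoint. The analysis is narrower than the endpoint stated in sections 1.1 and 3. It leaves out rehabilitation-center days in patients first discharged home, and it offers no between-arm view of readmission against which to read a lower count. On the assumption that the 41% applies, about 98 patients are analyzed for this endpoint and about 142 are not.

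A reader might go further and conclude that the endpoint's direction is unreliable, or that the X4 brace would be credited with a saving produced by complications. The documents do not support that. They give no readmission rate, no length of stay and no reason to expect a particular difference between arms, so neither the size nor the direction of any distortion can be derived. The primary endpoint, the sample size and the validity of the within-stratum comparison are not affected.

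**What to change.** Keep the planned within-stratum analysis of rehabilitation-center days. Add to sections 9.1 and 9.4.3:

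1. Rehabilitation-center days to postoperative day 56 in all ITT patients, compared by randomized arm, with discharge location in the model as already planned for outpatient visits. This also brings section 9 into line with sections 1.1 and 3.
2. A supportive report by arm, from the Daily Patient Log, of hospital readmission days and of rehabilitation-center plus readmission days. Any claim of reduced rehabilitation use should be read alongside it.

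Do not make such a claim formally conditional on the two counts pointing the same way. That rule has no error control: with no true effect on the total, it would be met about half the time.

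The cost is a few lines of SAP wording, one further count model and one descriptive table, all on data that every patient is already asked to log. There are two limits. The home stratum will hold many zeros, so the model must tolerate them; section 9.4.3 already allows alternatives where Poisson fits poorly. Hospital and rehabilitation days are not equal cost units, so the combined total should stay supportive.

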	 To evaluate provider satisfaction using the X4 brace with the Motion Intelligence platform
Endpoints:	Endnointe Drimany: Efficacy
	Encounts-Primary. Encacy
	scores, done preoperatively and at 8 weeks postoperatively between the control and study groups
	Endpoints-Primary: Safety
	To monitor the patient for any device related adverse events
	Endpoints -Secondary: Efficacy
	• To compare the number of inpatient days in a rehabilitation center
	 between the control and study groups To compare the number of outpatient visits to a physical therapy
	center between the control and study groups
	 To evaluate patients satisfaction with the X4 brace with the Motion Intelligence platform via the "System Usability Scale" (SUS) questionnaire (study group only)

	 To measure patient's compliance using the X4 brace with the Motion Intelligence platform by counting how many days they used the platform as prescribed within an 8 week period. A patient will be considered compliant if they use the platform once a day. To measure patient's adherence using the X4 brace with the Motion Intelligence platform. Adherence is defined as performing the entire exercise routine as prescribed once a day. To evaluate provider satisfaction with the X4 brace with the Motion Intelligence platform via the "System Usability Scale" (SUS) questionnaire (study group only)
Study Population:	240 female and male patients who have had unilateral total knee
Dhasa	arthroplasty by Drs. [name] or [name]
Phase:	4
Description of	
Darticipante:	Department of Orthonaedics, Succeet Hospital
Participants. Description of Study	Department of Orthopaedies, Sydsset Hospital
Intervention:	The X4 brace with the Motion Intelligence platform is intended to supplement the postoperative rehabilitation process for total knee arthroplasty (TKA). This "Virtual Rehabilitation" has the advantage of guiding the patient with their prescribed exercise regimen. Additionally, as this data is available to the surgical team on a daily basis this will allow the surgical team to intervene quickly when issues are identified.
Study Duration: Participant Duration:	The study is expected to take 1.5 years to complete Consent for participation in the clinical trial will be obtained at any time during the preoperative period. Patients will be in the study until they have completed their 8 week postoperative surgical office visit.

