6.4 STUDY INTERVENTION COMPLIANCE

Patients randomized to the X4 brace cohort are required to access the system twice daily. Patients who have not accessed the system for over 72 hours will be contacted to determine the reason for non-compliance.

Compliance and adherence with the X4 brace with the Motion Intelligence platform are secondary outcomes of this study.

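### X4-arm compliance and adherence have no planned estimate, and their only planned analysis, a home versus inpatient comparison, starts from a Poisson model that does not suit capped day counts

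*Combined protocol and SAP*

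**What the plan says.** The synopsis lists as a secondary objective "To evaluate patients compliance and adherence using the X4 brace with the Motion Intelligence platform", and section 6.4 confirms: "Compliance and adherence with the X4 brace with the Motion Intelligence platform are secondary outcomes of this study".

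Section 3 measures compliance "by counting how many days they used the platform as prescribed within an 8 week period". The synopsis adds "A patient will be considered compliant if they use the platform once a day", and section 9.1 makes this a daily rule: "a subject will be considered compliant if they access the platform at least once a day". For adherence, section 3 says "Adherence is defined as performing the entire exercise routine as prescribed once a day".

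Section 9.4.3 relates the number of compliant days, and separately the number of adherent days, to discharge location by Poisson regression within the X4 arm. If the fit is poor, other methods for counts are to be considered. Nothing else is planned for these two outcomes. Section 9.4.1 plans descriptive statistics for demographics, clinical characteristics and medical history. Section 9.4.3 specifies summary statistics for provider satisfaction.

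On frequency, section 9.1 states "Patients will be instructed to use the X4 brace twice a day" and section 6.4 states "Patients randomized to the X4 brace cohort are required to access the system twice daily". Section 6.1.1 (exercises) and section 8.1 (pain entry) also say twice a day.

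**The concern.** The objective asks how much X4 patients used the platform. The planned analysis asks whether home and inpatient patients differ, which is another question about a factor used for stratification and not assigned by randomization. A report that followed the plan exactly could give a p-value for that contrast and no overall figure for use, although level of use also bears on how any Knee Society Score result is read.

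The model is a second, smaller matter. A Poisson count has variance equal to its mean and no upper limit. Days of use are bounded by the follow-up period and cluster by patient, so their variance can lie well below or well above the mean. The plan gives no denominator of eligible days, although section 7.1 keeps patients who stop the brace in the study.

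There is also a wording conflict: the compliance count is described as use as prescribed, yet it credits a day after one access while several sections ask for two.

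**Working it through.** **The plan's own figure.** No figure is stated for compliance or adherence. The only design calculation is the primary sample size: 2 × (1.960 + 0.842)² × 27.5² / 10² = 118.7, so 119 per group by the normal approximation. The t-test gives 119.7, so 120 per group, with 80.1% power. The stated 120 per group for 80% power reproduces and does not depend on this point.

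**Inputs from the documents.** There are 120 X4 patients. About 41% go to rehabilitation (section 2.1), so 0.41 × 120 ≈ 49 inpatient and 71 home. The program runs 56 days and the average stay is 2 days (section 6.1.1), leaving about 54 days.

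**Assumed, because the documents are silent.** Mean daily use p = 70, 80 or 90%; within-patient correlation (ICC) ρ = 0 to 0.3.

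**Plain Poisson.** For beta-binomial counts over 54 days, the ratio of variance to mean is φ = (1 − p)(1 + 53ρ). Poisson assumes φ = 1. The rejection rate under no difference is therefore about 2Φ(−1.96/√φ). The last column is a simulation of the Poisson Wald test (20,000 runs).

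| Use | ICC | φ | 2Φ(−1.96/√φ) | Simulated |
|---|---|---|---|---|
| 70% | 0 | 0.30 | <0.1% | <0.1% |
| 70% | 0.1 | 1.89 | 15.4% | 15.1% |
| 70% | 0.3 | 5.07 | 38.4% | 38.1% |
| 80% | 0 | 0.20 | <0.1% | <0.1% |
| 80% | 0.1 | 1.26 | 8.1% | 8.1% |
| 80% | 0.3 | 3.38 | 28.6% | 28.3% |
| 90% | 0 | 0.10 | <0.1% | <0.1% |
| 90% | 0.1 | 0.63 | 1.4% | 1.4% |
| 90% | 0.3 | 1.69 | 13.2% | 13.3% |

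A Poisson model also puts 4.7% of its probability above 54 days at 80% use, and 19.7% at 90%.

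**With the fallback.** Suppose a Pearson fit check is followed by a dispersion-scaled test. If misfit in either direction triggers it, type I error is about 4-6%. If only overdispersion is checked, it is at most 5.8% but far below 5% when patients behave alike. Quasi-binomial regression on eligible days (53-55 per patient) gives 4.7-5.2%, and quasi-Poisson with an eligible-days offset 4.6-5.2%.

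**Power under an overdispersion-only check.** For use 5 points lower in inpatients at ICC 0.02, against quasi-binomial:

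| Use | No one stops the brace | 5% stop on a random day |
|---|---|---|
| 70% | 70 vs 83% | 55 vs 56% |
| 80% | 66 vs 91% | 53 vs 55% |
| 90% | 61 vs 99% | 50 vs 55% |

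**The missing estimate.** A whole-arm mean proportion has a 95% half-width of about 1.98 × √[p(1 − p)(1 + 53ρ)/(54 × 120)]. At 80% use this is 1.0, 2.5 and 4.0 percentage points at ICC 0, 0.1 and 0.3. Over the full assumed range it is 0.7 to 4.6 points, so the trial can answer its stated objective precisely.

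**Choice of denominator.** Section 7.2 lets the investigator withdraw a patient for significant non-compliance. Suppose 10% are withdrawn at day 14 after using 20% of those days, and the rest use 80%. Ending eligible days at withdrawal gives 0.9 × 80 + 0.1 × 20 = 74.0%. Counting to day 56 gives 0.9 × 80 + 0.1 × (0.20 × 14/56 × 100) = 72.5%. Ending at withdrawal removes the poorest users' later non-use.

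**The case against.** The strongest reply concerns the model. Section 9.4.3 already provides for a Poisson model that fits badly, and poor fit naturally includes too little variance as well as too much. Followed that way, the test holds close to 5%. This stands, so the table of plain Poisson error rates describes the first-choice model and not the plan as a whole.

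A reader might infer a serious loss of power. The documents do not support that. It needs a one-sided fit check that the plan does not state, patients who behave nearly alike, and almost no one stopping the brace. It mostly disappears at 5% stopping (an assumed share), and sections 6.4 and 7.1 foresee lapses and stopping.

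A reader might also infer that the once-a-day rule is hidden or ambiguous. It is neither. Section 9.1 sets it beside the twice-daily instruction, and no analyst could score a day two ways. For adherence, as prescribed can refer to the content of the routine. Only a wording edit remains.

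On the missing estimate, section 9.4.1 does not say that nothing else will be described, and a Poisson model with a single two-level factor yields mean days for each location. That is fair, but those means are a by-product. They are not a planned whole-arm estimate, a proportion of eligible days or a confidence interval. This part of the concern stands.

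**Conclusion.** The point holds as a cheap improvement. The main gap rests on the text alone: compliance and adherence are to be evaluated in the X4 arm, and no X4-arm estimate of either is planned. The second gap is that the first-choice model has the wrong variance for capped counts, with type I error from about 0% to about 40% for assumed use of 70-90% and ICC 0-0.3. The fallback largely repairs this if applied to misfit in either direction, but alternatives are only to be considered, and neither a fit check nor a model is named. All the modelling figures rest on assumed use, ICC and stopping rates, and on applying the 41% rehabilitation share to the trial. The outcomes are secondary and confined to one arm; the primary Knee Society Score analysis and the sample size are untouched.

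**What to change.** 1. In section 9.4.3, report for the whole X4 arm the mean proportion of eligible days compliant, and the mean proportion adherent, each with a 95% confidence interval.
2. For the home versus inpatient comparison of both outcomes, replace plain Poisson with quasi-binomial or beta-binomial regression on eligible days. Quasi-Poisson with an eligible-days offset is also valid.
3. Define eligible days in advance as brace issue to postoperative day 56 for every randomized X4 patient, and state the start day for anyone randomized who never receives the brace. Count days after stopping the brace, or after investigator withdrawal for non-compliance, as non-use. As a sensitivity analysis, end eligible days at withdrawal for other reasons.
4. Wording only: reconcile the as-prescribed description of compliance in sections 1.1 and 3 with the twice-daily statements in sections 6.1.1, 6.4, 8.1 and 9.1. The frequency is the sponsor's decision.

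The cost is edits to a few sections and one derived variable per patient, from brace-issue and withdrawal dates. No new data collection is needed. The downside is that reported use may look less favourable.
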